Notes: If timing of vaccination during pregnancy is specified as 'any', this means that women vaccinated at any point from six weeks preconception to date of end of pregnancy (E) will potentially be included in the analysis dependent on the woman being followed-up to the end of the outcome-specific follow-up period. For longer term risk periods: E is date of end of pregnancy; PP is mother's postpartum period, i.e. 6 weeks following delivery (E to E+41); NN is baby's neonatal period, i.e. 4 weeks following live birth (E to E+27). The pregnancy specific maternal outcomes listed above require follow-up to the end of the postpartum period (E+41) for mothers and the end of the postnatal period (E+27) for babies.

3.5.2: Exposure

The primary exposure to be investigated in the analyses is **any** receipt of COVID-19 vaccine from six weeks before conception to the end of an outcome-specific exposure period within pregnancy (Yes/No). The exposure periods for vaccination varies for each outcome (referred to as “outcome-specific exposure period” throughout this protocol), as outlined in Table 2. For ectopic pregnancy, for example, the exposed group will include women who were vaccinated between six weeks before conception up to 2⁺⁶ weeks gestation, while for stillbirth the vaccine exposure period is extended up to the end of the pregnancy.

Subgroup analyses will be conducted where sample size permits, further stratifying women who received their COVID-19 vaccine within the outcome-specific exposure period by: (1) the number of doses received; (2) by the class of vaccine(s) received and; (3) by the type of vaccine(s) received. For the latter two subgroup analyses, we will exclude women who received multiple different classes or types of vaccine within the outcome-specific exposure period. These results will need to be interpreted with caution given that some types of vaccination will be linked to specific sub-groups of women. For example, early in the vaccination programme women who were frontline health or care workers were more likely to receive the Pfizer/BioNTech vaccine, whereas women who were clinically (extremely) vulnerable were more likely to receive the AstraZeneca vaccine. There is therefore potential for residual confounding in comparative analyses examining outcomes following receipt of specific vaccine types.

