Maternal pre-pregnancy clinical vulnerability (excluding diabetes)	Clinically extremely vulnerable (on shielding list)	
	Clinically vulnerable (Q-COVID comorbidity excluded diabetes or hypertension)	
	Not clinically vulnerable	
Diabetes	Yes – pre-existing diabetes	If we only have a small number of women that are identified as having diabetes but it is unknown as to whether this is gestational or pre-existing, then we will combine gestational diabetes & unknown diabetes groups.
	Yes – gestational diabetes	
	Yes – diabetes onset unknown	
	No diabetes	
BMI at antenatal booking	Underweight (<18.5) Healthy weight (18.5-<25) Overweight (25-<30) Obese (30-<40) or severely obese (≥40) Unknown	Obese and severely obese will be combined.
Smoking at antenatal booking	Yes - current	
	Yes - former	
	No - never	
	Don't know	

Note: categories will be collapsed as required.

We have considered, but are currently not planning to include, several other covariates. These include parity and pregnancy-related complications other than gestational diabetes. Information on parity is only available on delivery records, negating its inclusion for any of the early pregnancy outcomes, and there are concerns about the quality of these data. Theoretically, pregnancy-related complications (e.g. pregnancy-induced hypertension and pregnancy-related bleeding) could be on the causal pathway between vaccination status and other adverse outcomes so will not be included as potential confounders. However, additional analyses will be conducted as appropriate if we see signals of associations between vaccination and outcomes that might be due to differential vaccination uptake in women with pregnancy-related complications. Gestational diabetes was considered as an exception to this and included as a covariate. This is because pregnant women with gestational diabetes were added to the list of individuals clinically vulnerable and therefore eligible for vaccination in priority risk group 6 early in the vaccination programme (March 2021), possibly leading to high uptake in this group, and the known association between diabetes and many of the outcomes under study.

3.6: Cohort study matching

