In addition, vaccinated pregnant women will also be matched by season of conception (quarter) to historical controls from the pandemic and pre-pandemic periods due to the seasonality of some outcomes. It is not necessary to do this for contemporary controls (from the pandemic vaccination period) as those pairs will be matched by calendar date (i.e. matching a vaccinated woman by maternal and gestational age, on the day of vaccination to a control of the same maternal and gestation age, on the same date).

For comparisons between vaccinated and unvaccinated matched individuals, the index date (reference point for matching maternal and gestational age, and season of gestation for analyses involving controls from historical periods only) will be the date of vaccination.

⁵ Donegan K, King B, Bryan P. Safety of pertussis vaccination in pregnant women in UK: observational study BMJ 2014; 349:g4219 doi:10.1136/bmj.g4219. Available from: <https://www.bmj.com/content/349/bmj.g4219>

The matching strategy for each of the three analyses is shown in Table 5.

Table 5: Matching strategy for each analysis of the matched cohort study

Analysis	Time period for control group*	Matched three controls to each case by:	Notes
Primary analysis	Pre-pandemic period (01 January 2015 to 29 February 2020)	
 Maternal age Gestational age Season of conception (quarter) 	
 Aim to match to three unvaccinated controls Maternal age matched by ± 1 year but relaxed at tails of maternal age distribution Gestational age matched by same week but relaxed at tails of the gestation distribution
Supplementary analysis 1	Pandemic vaccination period (from 08 December 2020 to date of data extraction), excluding cases and controls with confirmed COVID-19 between six weeks preconception to end of outcome-specific follow-up period	
 Maternal age Gestational age 	
Supplementary analysis 2	Pandemic vaccination period (from 08 December 2020 to date of data extraction), including cases and controls with confirmed COVID-19 between six weeks preconception to end of outcome-specific follow-up period	
 Maternal age Gestational age 	

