First, a model with no covariates will be fitted to calculate the unadjusted OR for the association between vaccination status and each outcomes of interest. Subsequently, we will calculate an adjusted OR for the association between vaccination status and each outcomes of interest, by adding all covariates to the model (Table 4). P-values and confidence intervals will be reported for all models. For some rarer outcomes, we will adjust our modelling approach as required (e.g. re-classification of groupings or removing insignificant covariates). Covariate pairs will be assessed for collinearity before adding to the model. For any covariate pairs that are highly correlated, only the covariate which has the biggest impact on the association between the exposure and outcome will be included in the model.

As previously described (section 3.5.2), analyses will be conducted first looking at the association between having any vaccination and outcomes, and then in sub-group analyses stratified by vaccine classes and individual vaccine types;

- Vaccine type: Pfizer, AstraZeneca, Moderna, Janssen
- Vaccine group: Pfizer and Moderna (mRNA); AstraZeneca and Janssen ((adeno)virus vector)
- Number of vaccine doses

Our main analyses will include all pregnancies/births, regardless of whether there is evidence that it was singleton or multiple, with sensitivity analyses conducted restricting to only pregnancies/births where there was no evidence it was a multiple. We often do not know whether pregnancies which end early (e.g. due to miscarriage) were singleton or multiple, hence the decision to only include pregnancies with *no evidence* of being a multiple in these sensitivity analyses.

4.5: Additional analyses

There are two further analyses that may subsequently be conducted to assess the association between vaccination and adverse outcomes, specifically:

1. We will consider using all data from the pre-pandemic period to predict the expected number of outcomes among the vaccinated pregnant women, and compare this predicted number to the observed number within the vaccinated group of women.
2. For rarer outcomes (e.g. for congenital anomalies, microcephaly), we will consider a nested case control study if signals are identified in this present matched cohort analysis but wide confidence intervals due to the small number of events negate any meaningful conclusions. This design maximises power to assess any association between vaccination and these rare outcomes.

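### Gestational diabetes enters the adjusted miscarriage and ectopic pregnancy models with no requirement that it was recorded before the index date, so in those models it marks pregnancies that lasted longer

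*Protocol*

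**What the plan says.** Section 3.5.3 explains why complications such as pregnancy-induced hypertension and bleeding are left out: they "could be on the causal pathway between vaccination status and other adverse outcomes so will not be included as potential confounders". It then makes one exception: "Gestational diabetes was considered as an exception to this and included as a covariate". Two reasons are given. First, "pregnant women with gestational diabetes were added to the list of individuals clinically vulnerable and therefore eligible for vaccination in priority risk group 6", from March 2021. Second, diabetes is known to be associated with many of the outcomes.

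Table 4 lists diabetes as pre-existing, gestational, onset unknown or none. No date or gestation limits the gestational level. Other rows of the table are anchored: clinical vulnerability is pre-pregnancy, and BMI and smoking are taken at antenatal booking.

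Section 4.4 fits an unadjusted model first, then obtains the adjusted OR for each outcome "by adding all covariates to the model (Table 4"). It allows departures: "For some rarer outcomes, we will adjust our modelling approach as required (e.g. re-classification of groupings or removing insignificant covariates"), and only one of a highly correlated pair of covariates is kept. Miscarriage and ectopic pregnancy go into a conditional multinomial model whose reference is live birth or ongoing pregnancy.

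Exposure runs "from six weeks before conception to the end of an outcome-specific exposure period within pregnancy" (section 3.5.2). In Table 2 that period ends at 2+6 weeks for ectopic pregnancy, 13+6 for first-trimester miscarriage and 23+6 for miscarriage overall. Under section 3.6 the index date "will be the date of vaccination".

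**The concern.** A confounder has to be fixed before exposure, or at least must not depend on the outcome. As Table 4 is written, the gestational level fails this for early losses. A woman whose pregnancy ends at 8 weeks has little chance of acquiring the code; a woman whose pregnancy continues has the rest of it in which to do so. Adjusting for the code then amounts to removing some event-free women from the comparison. If the share removed differs between vaccinated women and controls, the vaccine OR moves even when vaccination does nothing.

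The eligibility reason does not cover these models. It makes gestational diabetes a cause of vaccination only when the diagnosis comes first. That can hardly happen for a vaccination by 2+6 weeks, and it is a weak argument for one by 13+6.

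The section recognises a related limit for parity: "Information on parity is only available on delivery records, negating its inclusion for any of the early pregnancy outcomes". The parallel is partial, since parity is dropped from all models and data quality is a second ground. But the thought that a variable known only later cannot serve an early outcome is there, and it is not carried over to gestational diabetes.

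At stake is a spurious shift in the adjusted miscarriage OR of a vaccine-safety study whose primary controls come from 2015 to 2020.

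**Working it through.** The protocol gives no figure on this point to reproduce, and no prevalence of gestational diabetes. All prevalences below are assumptions.

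**Limit of the adjusted OR for an early loss**

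Suppose that the risk of loss is p in both groups (true OR 1), and that no woman with a loss is coded gestational. Among continuing pregnancies a share g1 (vaccinated) or g0 (controls) is so coded. The gestational stratum has no events, so its coefficient tends to minus infinity and it carries no information on vaccination. In the remaining women:

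- odds, vaccinated = p / [(1-p)(1-g1)]
- odds, controls = p / [(1-p)(1-g0)]
- adjusted OR = (1-g0)/(1-g1), whatever the value of p

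| g0 (controls) | g1 (vaccinated) | OR under no effect | log OR |
|---|---|---|---|
| 5% | 5% | 1.00 | 0 |
| 4% | 6% | 0.96/0.94 = 1.021 | 0.021 |
| 5% | 8% | 0.95/0.92 = 1.033 | 0.032 |
| 5% | 10% | 0.95/0.90 = 1.056 | 0.054 |
| 8% | 5% | 0.92/0.95 = 0.968 | -0.032 |

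The direction follows whichever group has more recorded diagnoses.

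**Check in the matched model**

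Conditional logistic regression was simulated on 1:3 sets with 12% miscarriage and true OR 1. At 5% v 8%, the adjusted OR divided by the unadjusted OR averaged 1.032 over 597 data sets of 1,500 sets each, against 1.033 from the formula. Single runs of 10,000 sets gave ratios of 1.00 at 5% v 5% and 1.06 at 5% v 10%. These are binary models; the planned multinomial model was not simulated.

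**Size against sampling error**

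Section 3.7 expects 5,000 vaccinated women and 15,000 controls by the end of 2021. Take 15% miscarriage, the middle of Table 2's 10 to 20%:

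SE = sqrt(1/750 + 1/4250 + 1/2250 + 1/12750) = 0.046

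The shifts from 4% v 6% to 5% v 10% are then 0.021/0.0457 = 0.5 to 0.054/0.0457 = 1.2 SE.

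This is an upper view. Controls are matched at the gestation of vaccination, so only the risk remaining after that point counts. At an assumed remaining risk of 5%:

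SE = sqrt(1/250 + 1/4750 + 1/750 + 1/14250) = 0.075

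The same shifts are then 0.3 to 0.7 SE. At 5% v 8%, a nominal 5% two-sided test rejects with probability about 11% in the first case (shift 0.70 SE) and about 7% in the second (0.43 SE). Fewer than 5,000 women vaccinated before 24 weeks would lower both.

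**Later outcomes**

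For a woman vaccinated before diagnosis, the covariate is a post-exposure event. An expected-count logistic model was used, with 7% baseline outcome risk, 6% gestational diabetes, an OR of 1.5 from gestational diabetes to outcome, and an unmeasured common cause of both (all assumed).

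| Effect of vaccination on gestational diabetes (RR) | Total-effect OR | OR adjusted for gestational diabetes |
|---|---|---|
| 0.8 | 0.994 | 1.002 |
| 1.0 | 1.000 | 1.000 |
| 2.0 | 1.031 | 0.990 |

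With no effect of vaccination on gestational diabetes there is no distortion. Otherwise adjustment removes, or slightly reverses, a small mediated effect.

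**The case against.** **The exception is deliberate.** Section 3.5.3 weighs the causal-pathway argument and sets it aside because a diagnosis opened access to vaccination. For outcomes with exposure up to the end of pregnancy this stands: for women diagnosed before vaccination, adjustment is the confounder control intended. It does not reach early-loss models.

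**The size rests on assumed prevalences.** This stands. Nor can priority access be used to argue for a large g1 in these models: a diagnosis made after the window closes cannot have prompted a vaccination inside it. What remains is a difference in era, recording or case mix. Age is matched, BMI and ethnicity are adjusted for, and the two supplementary analyses use contemporary controls, which removes the era difference there. But the primary analysis uses pre-pandemic controls, and equal prevalence is untested.

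**The protocol has ways out.** Categories may be collapsed, collinear covariates dropped and models for rarer outcomes simplified. The last might reach ectopic pregnancy (1.0% background risk) but not clearly miscarriage. None of these clauses turns on timing.

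**Covariate dating belongs in an analysis plan.** Often so. Here, however, the protocol fixes a rule, all Table 4 covariates in each adjusted model, and followed as written it conditions on the pregnancy continuing.

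A reader might infer more than the document supports:

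- That every model is affected. Only adjusted models are; the unadjusted OR comes first, so a shift on adjustment would be visible.
- That every woman coded gestational had passed the miscarriage window. The document does not say when diagnosis occurs.
- That later-outcome effects are adjusted away. That requires vaccination to alter gestational diabetes risk, and nothing in the protocol suggests that it does.

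**Conclusion.** The point holds for the adjusted miscarriage and ectopic pregnancy models. Gestational diabetes has no time anchor, it enters those models by rule, and the eligibility argument for including it applies only when diagnosis precedes vaccination. For ectopic pregnancy the link to survival is nearly structural. For miscarriage it depends on the assumption that diagnosis is mostly mid-pregnancy or later.

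The likely size is modest: a factor of about 1.02 to 1.06 on the OR over the assumed prevalences, below 1 if controls have the higher prevalence, and exactly 1 if the prevalences are equal. Against sampling error that is roughly 0.3 to 1.2 SE, depending on the miscarriage risk remaining at vaccination. The defect in the rule is definite; its magnitude is uncertain. For later outcomes the matter is secondary, since distortion arises mainly if vaccination affects gestational diabetes. The change is worth making because it is cheap and the affected outcome is one where a small false signal would matter.

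**What to change.** In Table 4 and section 4.4:

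1. For miscarriage, its first- and second-trimester subtypes, and ectopic pregnancy, adjust for pre-existing diabetes v none.
2. For all other outcomes, code gestational diabetes only if it was recorded before the index date (the vaccination date, or the matched date for controls). Otherwise code by pre-existing status.
3. Where the diagnosis carries no date, report later outcomes with and without the current coding.

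Appendix 3 takes its covariates from the vaccination analysis, so the same rule should be stated there with the infection date as index.

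The cost is one derivation rule and a few lines of text. The early-loss distortion disappears by construction, and the intended control for women diagnosed before vaccination is kept. The downside is some loss of confounder control for later outcomes where gestational diabetes is undated, which the paired reporting in item 3 makes visible.

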For the matched cohort study, the primary comparison for each outcome will be between women vaccinated in the six weeks preceding conception or up to the end of the outcome-specific exposure period within pregnancy and unvaccinated pregnant women from the pre-pandemic period. Only women who had been followed-up to the end of the outcome-specific follow-up period on the 29 February 2020 are eligible to be controls for that outcome analysis. Women who have COVID-19 infection from six weeks preconception up to the end of the outcome-specific follow-up period will

not be eligible for inclusion in the vaccinated group for this primary analysis. Each individual in the pregnant vaccinated cohort will be matched to three individual unvaccinated pregnant controls, if possible⁵. Different pregnancies from a single woman can be matched to different cases, and if a case had a pregnancy in the pre-pandemic period, that pregnancy is a valid control, as long as the woman is not matched to herself. Here the assumption is that pregnancies are independent. A sensitivity analysis will be conducted, removing women who are vaccinated in the six weeks preconception – and her controls – from the analysis.

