With the pre-pandemic period being used as the baseline, there is an assumption that the pandemic has not substantially affected the outcomes of interest through, for example, changes in engagement and provision of maternity services. To investigate this, a supplementary analysis will be conducted with pregnant unvaccinated controls from the pandemic vaccination period (from 08 December 2020 to date of data extraction). In this supplementary analysis, we will exclude women (from both the vaccinated and unvaccinated group) who had any record of COVID-19 infection from six weeks preconception to the end of the outcome-specific follow-up period. However, given that there is potential for vaccination to impact on maternal, pregnancy and neonatal outcomes by changing the risks of acquiring COVID-19 and experiencing severe illness, we will also conduct a second supplementary analysis with pregnant unvaccinated controls from the pandemic. In this, we will retain both vaccinated and unvaccinated women with a confirmed record of COVID-19 infection during pregnancy and preceding the end of the outcome-specific follow-up period. For both these supplementary analyses, women who were vaccinated >6 weeks pre-conception will be included in the control group (as not vaccinated in pregnancy), however sensitivity analyses (if sample size permits) will be conducted to investigate any differences between pairs where the control is completely unvaccinated versus pairs where the control received vaccination >6 weeks pre-conception (e.g. vaccinated pre-‘pregnancy’). Additional supplementary analyses removing women who are vaccinated in the six weeks preconception will be considered for the analyses using women from the pandemic period as controls, if we observe an impact of removing these women in the primary analysis using pre-pandemic controls.

Maternal and gestational age are known to be important risk factors for adverse events in pregnancy (e.g. miscarriage strongly influenced by maternal age). Consequently, the cohorts will be matched by maternal age (± 1 years but relaxed (i.e. possibly $\pm >1$ year) at the tails of maternal age distribution as fewer individuals available for matching), and gestational age (exact match, i.e. same week however allow for relaxation of this at the tails of the gestation distribution).

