Matching	
There will be three main analyses for all outcomes, each with a different set of inclusion criteria for the matching process, as follows:
 
Match 1 (primary): Exposed: women who had COVID-19 infection during the pandemic widespread testing period from six weeks preconception or in pregnancy but before the end of the outcome-specific exposure period, excluding any women who received vaccination for COVID-19 from six weeks preconception to the end of the outcome-specific follow-up period. Unexposed group: women from the pre-COVID-19 time period who had been followed-up to the end of the outcome-specific follow-up period by the 29th February 2020, matched to exposed women on maternal age, gestational age and season of conception.
 
Match 2:

	
Exposed: women who had COVID-19 infection during the pandemic widespread testing period from six weeks preconception up to the end of the outcome-specific exposure period, excluding any women who received vaccination for COVID-19 from six weeks preconception up to the end of the outcome-specific follow-up period.
 
Unexposed group: women from the pandemic widespread testing period who did not have confirmed COVID-19 infection from six weeks preconception up to the end of outcome-specific exposure period and did not receive vaccination for COVID-19 from six weeks preconception to the end of the outcome-specific follow-up period, matched to exposed women by maternal age, gestational age, and date of infection.
 
Match 3:
 
Exposed: all women who had COVID-19 infection during the pandemic widespread testing period from six weeks preconception up to the end of the outcome-specific exposure period (i.e. including any women who received vaccination for COVID-19 at any time).
 
Unexposed group: women from the pandemic widespread testing period who did not have confirmed COVID-19 infection from six weeks preconception up to the end of the outcome-specific exposure period (i.e. including any women who received vaccination for COVID-19 at any time), matched to exposed women on maternal age, gestational age, and date of infection.

Analytical approach	Same analytical approach as for vaccination exposure (described in Section 4).

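### Eligibility depends on infections and vaccinations after the index date, over a window that for most outcomes ends with the pregnancy, so shorter pregnancies are preferentially kept, in the primary analysis on the vaccinated side only

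*Protocol*

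**What the plan says.** **Index date.** Section 3.6 matches on maternal and gestational age at an index date that "for analyses involving controls from historical periods only) will be the date of vaccination".

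**Primary analysis (section 3.6).** The comparison group is "unvaccinated pregnant women from the pre-pandemic period". The infection rule opens "Women who have COVID-19 infection from six weeks preconception up to the end of the outcome-specific follow-up period will". It applies to one side only, since such women would "not be eligible for inclusion in the vaccinated group for this primary analysis".

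**Supplementary analysis 1 (section 3.6, Table 5).** Controls come from the pandemic vaccination period, and the infection rule covers both sides: "we will exclude women (from both the vaccinated and unvaccinated group) who had any record of COVID-19 infection from six weeks preconception", with the window closing when outcome-specific follow-up ends. Supplementary analysis 2 keeps infected women.

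**Control definition in both supplementary analyses.** "women who were vaccinated >6 weeks pre-conception will be included in the control group (as not vaccinated in pregnancy"). Section 3.3 counts a woman as vaccinated if she received a dose at any time up to the end of pregnancy. Section 3.5.2 makes exposure a yes/no variable over the whole outcome-specific exposure period.

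**Appendix 3 (infection as exposure).** The exposed group in Matches 1 and 2 is formed "excluding any women who received vaccination for COVID-19 from six weeks preconception to the end of the outcome-specific follow-up period". The unexposed in Match 2 are women "who did not have confirmed COVID-19 infection from six weeks preconception up to the end of outcome-specific exposure period and did not receive" (the object is a COVID-19 vaccine, up to the end of follow-up). The unexposed in Match 3 are screened on infection only.

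**Window length.** Table 2 and its notes end follow-up at end of pregnancy (E), E+27 or E+41 for most outcomes. Miscarriage and preterm birth have gestational limits instead (23+6 and 36+6).

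**Analysis.** Section 3.5.1 sets time to event aside in the main analyses, and section 4.4 specifies conditional logistic or multinomial regression.

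**The concern.** Matching makes the groups comparable on the index date. Eligibility is then decided partly by what happens later, and the time available for that differs with the outcome. A vaccinated woman whose pregnancy ends soon after the index date has little time to be infected and stays in. One who carries to term has months in which to be removed. The retained vaccinated women are therefore enriched for short pregnancies, and a binary-outcome model has no means of undoing this.

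In the primary analysis the historical controls cannot have had COVID-19, so no matching selection occurs on their side. The primary safety estimate could show a spurious excess for outcomes that go with short gestation. In the pandemic-control analyses the selection may act on the controls instead, giving apparent protection. If both operate, disagreement between the primary analysis and Supplementary analysis 1 is hard to read, although Supplementary analysis 1 is the planned check on whether the pandemic itself changed outcomes. Section 5 does not list this among the limitations.

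**Working it through.** The protocol gives no figure to reproduce here, and no infection or uptake rates. The rates and gestations below are assumptions, and there is no true effect throughout.

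**Formula.** Let h be the weekly rate of the event that removes a woman, and t1 and t0 the weeks from index date to window close for women with and without the outcome. The proportion kept is exp(−h·t). If outcome risk is p, the odds among kept women are p·exp(−h·t1) / [(1−p)·exp(−h·t0)]. With no screen on the other side, the odds ratio (OR) is exp(h·Δ), where Δ = t0 − t1; p cancels. If only the controls are screened, it is exp(−h·Δ).

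**Miscarriage, primary analysis, window closing at pregnancy end.** Index at 8 weeks and loss 3 weeks later; women without loss are followed 16 weeks to 24 weeks. Δ = 16 − 3 = 13.
- h = 0.25%: exp(0.0325) = 1.03
- h = 0.5%: exp(0.065) = 1.07
- h = 1%: exp(0.13) = 1.14

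If the window runs to 23+6 for everyone, Δ = 0 and the OR is 1.00.

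For scale, with a true risk of 8% in both groups and h = 1%, the vaccinated odds become 0.0870 × 1.139 = 0.0990, a risk of 9.0%. At the section 3.7 sample sizes, a two-sided 5% test of two proportions would call this significant about 61% of the time (5,000 v 15,000) or 88% (10,000 v 30,000). Those sizes are for all vaccinated women; fewer will have been vaccinated before 24 weeks.

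**Stillbirth, primary analysis.** Table 2 ends the window at E, so no reading is needed. If stillbirths occur on average 7.5 weeks before the end of other pregnancies (32 v 39.5 weeks), h = 0.5% gives exp(0.0375) = 1.04 and h = 1% gives exp(0.075) = 1.08.

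**Preterm birth, primary analysis.** Follow-up stops at 36+6. For delivery at 34 weeks, Δ is about 3 weeks, not the 5.5 weeks to a 39.5-week delivery. h = 1% gives exp(0.03) = 1.03 and h = 3% gives exp(0.09) = 1.09. Again it is 1.00 if the window runs to 36+6 for everyone.

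**Supplementary analysis 1, infection screen.** With both sides screened, OR = exp[(h_vaccinated − h_control)·Δ]. Equal rates give 1.00. If vaccination halves a 1% rate, miscarriage gives exp(−0.005 × 13) = 0.94.

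**Supplementary analyses 1 and 2, later vaccination of controls.** If a later dose disqualifies a control and uptake is 1% per week, miscarriage gives exp(−0.13) = 0.88.

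**Appendix 3.**
- Match 1: only the exposed are screened, on later vaccination. At 1% per week and Δ = 13, with the window closing at pregnancy end, OR = 1.14.
- Match 2: the vaccination screen covers both sides and gives 1.00 at equal rates. The later-infection screen covers the unexposed only and pulls the OR below 1.
- Match 3: only the unexposed are screened, on later infection, with the same downward pull.

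**The case against.** **The direction is not uniform.** This stands. Hypertensive disorders are diagnosed only after 20 weeks, so keeping more early losses adds women who could not have the outcome and can lower vaccinated risk. Excluding infected women also removes outcomes caused by infection, which pulls the vaccinated risk down and is not in the formula.

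**The window may be the same for everyone.** For miscarriage and preterm birth, Table 2 gives gestational limits. If infection is looked for up to that limit whenever the pregnancy ended, the bias disappears. Section 3.5.1 asks for completed follow-up only from women without the outcome, which hints that follow-up stops at the event, but the protocol does not settle it. Outcomes whose window ends at E, E+27 or E+41 are not rescued by this argument.

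**The rule for later-vaccinated controls is not written down.** This also stands. The quoted sentence explains why women vaccinated long before conception may be controls. The bar on women vaccinated after the index date follows from reading sections 3.3, 3.5.2 and 3.6 together; it is a strong inference, not a stated rule.

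**Stronger readings a reader might reach.**
- That both groups are selected on later events throughout. The primary analysis and Match 1 screen only the exposed, and two of the two-sided screens cancel at equal rates.
- That a woman infected at 30 weeks is removed while a loss at 9 weeks is kept, so that pregnancy-loss risk is inflated. No single loss outcome contains that contrast: miscarriage follow-up stops at 23+6 and stillbirth starts at 24+0.
- That the supplementary analyses cannot serve their purpose at all. Supplementary analysis 2 has no infection screen. It exists because the protocol already recognises that vaccination changes infection risk.

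**Conclusion.** The concern holds in a limited form. Eligibility uses events after the index date, for most outcomes over a window tied to the length of the pregnancy, and nothing in the planned analysis corrects for it. It is clearest in the primary analysis and in Appendix 3 Match 1, where the historical controls cannot fail the screen. There it tends to inflate exposed-group risk for stillbirth, neonatal death and low Apgar score. For miscarriage and preterm birth it does so only if the window closes at pregnancy end. For late-onset maternal outcomes the sign may reverse.

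The size rests on assumed rates. At infection rates of 0.25% to 0.5% per week the primary miscarriage OR shifts by 3% to 7%; at 1% it shifts by 14%. Preterm birth shifts by about 3% at 1%. Later vaccination of controls at 1% per week would move the miscarriage OR to about 0.88, if the implied rule is the one applied. The bias is small at low rates, and could pass for a safety signal or a benefit in early-pregnancy outcomes at higher ones. Excluding infections before the index date is ordinary baseline restriction and is not in question.

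**What to change.** In section 3.6, Table 5 and Appendix 3:
1. Apply infection and vaccination exclusions using history up to the index date only.
2. State that a pandemic-period control qualifies if unexposed on the matched index date, whatever happens later.
3. If an infection-free primary analysis is wanted, close its exclusion window at the same fixed gestational or calendar point for every woman, whenever the pregnancy ended. Report the version excluding only pre-index infections alongside it.
4. Add this selection to the limitations in section 5, with its expected direction by outcome group.

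A time-to-event model that censors at later vaccination or infection is a reasonable optional sensitivity analysis. It is not required, given the deliberate choice of a binary-risk design.

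The cost is protocol wording and re-coding; vaccination dates and linked PCR test data are already planned for the study database. The price is that some post-index infections, and some controls vaccinated later, stay in the analysis and may dilute the contrast.
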